**Group CBT for PTSD: A RCT with veterans**

**PI: [name].**

**NCT01544088**

**Date: December 28, 2016**

## Project Narrative

### **A. Specific Aims:**

Considerable attention has focused recently on the treatment of PTSD. At present, strong empirical evidence exists to support the efficacy of Cognitive Behavioral Treatments (CBT) when used in an individual format to treat PTSD following trauma. However, the development and testing of group treatment approaches for PTSD has lagged. Recently, [name] (a Co-I of this proposal) completed a treatment development grant (R21 MH64777) that designed and provided preliminary support for a Group CBT (GCBT) to treat PTSD. Pilot data suggested strong initial support for this treatment with survivors of serious motor vehicle accidents diagnosed with PTSD. The overall objective of this proposal is to test this GCBT with veterans. The proposed project encompasses **two specific aims**.

The project will consist of a randomized controlled trial with 196 cases, in which participants will be randomly assigned to (a) Group CBT (GCBT,  $n = 98$ ) or (b) *Supportive Group Psychotherapy (SGP, n = 98)*. Outcome data will be collected at pre-treatment, mid-treatment, post-treatment, and *three times* during a 12-month follow-up. This application is a hybrid efficacy-effectiveness trial, in keeping with current translational emphasis on producing information about treatment outcomes that generalize to “real life” settings.

**The primary specific aim** is to examine if GCBT produces significant reductions in PTSD relative to the *SGP* condition, and to determine if these changes are durable across a *12-month* follow-up interval. Two hypotheses are proposed:

**Hypothesis 1.** Patients with PTSD who receive GCBT will show greater reductions in PTSD-related symptoms, relative to patients who receive *SGP*, at post-treatment assessment, a between-group difference that will persist through *3 and 6 month follow-up*.

**Hypothesis 2.** Reductions in PTSD symptom severity will be maintained in the GCBT group at *12-month* follow-up.

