**The secondary specific aim** is to examine the generalizing effects of both GCBT and *SGP* on distress, impairment, and co-morbid conditions (particularly generalized anxiety, depression, and substance use). Because most trials in the PTSD literature do not include a thorough assessment of treatment generalization, it is unknown whether available treatments only address PTSD or whether gains generalize to other domains. Three hypotheses are proposed:

**Hypothesis 3.** For veterans who are diagnosed with co-morbid Major Depressive Disorder (MDD), Generalized Anxiety Disorder (GAD), and/or Alcohol abuse prior to treatment, GCBT will produce significantly larger symptom reductions for these conditions, relative to *SGP* at post-treatment assessment and these generalized changes will show stability at *6-month* follow-up.

**Hypothesis 4.** Patients who receive GCBT will report less distress and impairment, relative to patients who receive *SGP*, at post-treatment assessment, a between-group difference that will persist through *3 month* follow-up.

**Hypothesis 5.** Gains in these domains (distress and impairment) will be maintained in the GCBT group at the *12-month* follow-up.

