#### **D. 4. Measures**

The hypotheses state that relative to participants who are assigned to the *SGP* condition, participants who receive GCBT will show greater reductions in PTSD symptoms, report less utilization of health-care resources, and report less distress and impairment, at post-treatment

and 3 and 6 month follow-up assessments. Additionally, for patients with co-morbid Major Depressive Disorder (MDD), Generalized Anxiety Disorder (GAD), and/or Alcohol abuse prior to treatment, GCBT will produce significantly larger symptom reductions for these conditions, relative to *SGP* at post-treatment assessment and 3- and 6- month follow up. As well, gains in PTSD symptoms, distress and impairment will be maintained in the GCBT group at 12-month follow-up.

Measures selected to evaluate these hypotheses are described in the next section (see also Table 4).

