#### **D.7.a Analyses to Test Specific Aims:**

The **primary specific aim** of this project is to examine if GCBT produces significant reductions in PTSD relative to the *SGP* condition and to determine if these changes are durable across a 12 -month follow-up interval. Two hypotheses will be tested.

**Hypothesis 1.** Patients with PTSD who receive GCBT will show greater reductions in PTSD-related symptoms relative to patients who receive *SGP*, at post-treatment assessment, a between-group difference that will persist through 6 month follow-up. To test this hypothesis, we will use multilevel latent growth modeling. Whereas a traditional latent growth model approach would suffice in many instances (e.g., when patients are treated individually), as noted earlier, the delivery of treatment in group format is likely to result in the violation of the assumption of independent observations (i.e., within-group similarity on treatment outcomes and process variables; cf. Schnurr et al., 2001, 2003). In initial analyses, we will evaluate the

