extent of dependency (i.e., clustering) by calculation of intraclass correlations (ICCs) using variance estimates from unconditional cell means models of key outcome variables (cluster = treatment group). Our proposed  $N$  of 196 will be clustered into 14 treatment groups per condition. Assuming non-zero ICCs, a multilevel approach will be incorporated into the latent growth framework in order to obtain correct standard errors, test statistics, and confidence intervals. In the traditional multilevel modeling, the design would be construed as a three-level model; i.e., repeated observations (Level 1) nested under individuals (Level 2), individuals nested under treatment groups (Level 3). However, because the first two levels are combined in the multivariate framework of latent growth modeling, this design can be characterized as a two-level model (i.e., latent growth factors are nested under treatment groups) where time-invariant covariates (i.e., dummy codes for treatment condition) are included to account for the within-group and between-group variability in initial status (pre-treatment) and symptom change (improvement over active treatment and follow-up). In the latent growth model portion of the models, the intercept will be centered on pre-treatment (i.e., first slope loading will be fixed to 0.0). Because there is no substantive interest in the form of the growth trajectory, intermittent time points (i.e., slope factor loadings) will be freely estimated and the final timepoint of interest (e.g., post-treatment) will have a corresponding factor loading fixed to 1.0. Accordingly, the mean and variance of the slope will convey the fixed (average) and random effects (individual differences) of change for the given time interval of interest. The Level 2 variables of treatment condition (single dummy code using *SGP* as reference group) will be included as predictors to account for individual differences in treatment response and variability in outcome across treatment groups. To examine pre-treatment differences between treatment conditions, the intercept (centered on pre-treatment) will be regressed onto the treatment covariates (i.e., significant paths are indicative of differences in pre-treatment levels as a function of treatment condition). Any pre-treatment differences will be accommodated into the interpretation of findings and in the parameterization of the models (e.g., regression of the slope onto the intercept, as well as covariates such as treatment condition). The dependent variable for this analysis is the CAPS total score. Additionally, PCL will be examined, using the same analytic approach, in order to examine respondent effects (interviewer-rated versus self-report).

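### Hypothesis 1 has no stated model or rule for a persisting arm difference; its single-slope model, if run to 6 months, would force the arm differences in change to be proportional across visits

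*Combined protocol and SAP*

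**What the plan says.** Section D.7.a words Hypothesis 1 as greater PTSD symptom reduction under GCBT at post-treatment, "a between-group difference that will persist through 6 month follow-up". Section A gives the follow-up part as "3 and 6 month follow-up". Section D.4 likewise claims the arm differences at post-treatment "and 3 and 6 month follow-up assessments".

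The analysis is a multilevel latent growth model. The first slope loading is 0; then "intermittent time points (i.e., slope factor loadings) will be freely estimated and the final timepoint of interest (e.g., post-treatment") has its loading fixed at 1. There is one slope factor, which conveys the mean and variance "of change for the given time interval of interest". A single treatment dummy, with SGP as reference, predicts the growth factors, so as to account for initial status and "symptom change (improvement over active treatment and follow-up"). Both growth factors are nested under treatment groups. The section disclaims interest in the shape of the trajectory.

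The only path whose significance is interpreted is the regression of the intercept on treatment, which is a pre-treatment difference. No 6-month version of the model is written out for Hypothesis 1, and no contrast or decision rule is attached to persistence.

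Two neighbouring analyses do not fill the gap. Hypothesis 2 has an explicit test (equal 6- and 12-month loadings), but it concerns GCBT and drops the treatment covariate. Section D.7.d reports PTSD diagnosis percentages and reliable change by arm at follow-up visits, with no stated between-arm test.

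**The concern.** Persistence is half of the primary hypothesis, and it is a claim about how the arm difference moves over time. One slope with one treatment coefficient has no term for such movement. An analyst who follows the most natural 6-month reading would fix the last loading at 6 months, keep the visits in between, and read the slope-on-treatment coefficient as the 6-month effect. That coefficient borrows from the earlier visits through the shared loadings. It could therefore report a lasting benefit that has gone. If the same model also served the post-treatment claim, it could hide a real post-treatment difference.

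**Working it through.** **Plan's own figure.** None exists for persistence. The power section's d = 0.50 names no visit.

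**Inputs from the plan.** d = 0.50, ICC 0.11, groups of 7, 14 groups per condition, alpha 0.05 (sidedness not stated; two-sided assumed).

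**Assumed.** The mean trajectories below, in SD units. Unit variance at each visit. Three within-person correlation structures: compound symmetry 0.6, autoregressive 0.7, random intercept and slope. A group effect of 0 at baseline, half size at mid-treatment and full size from post-treatment. Complete data.

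**Algebra.** Write y_t = i + λ_t·s, with i = m + g·Trt and s = a + b·Trt, λ_pre = 0 and λ_6mo = 1.

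- Arm difference in change at visit t = b·λ_t.
- At 6 months it equals b. If that is 0, then b = 0 and the difference in change is 0 at every visit.
- The exception is mean change of zero at 6 months, where fixing that loading at 1 no longer sets a usable scale.

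Equivalently, change at post-treatment divided by change at 6 months must equal λ_post in both arms.

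**Assumed means (pre, mid, post, 3 months, 6 months) and the ratio post / 6 months.**

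| Case | SGP | GCBT | SGP ratio | GCBT ratio |
|---|---|---|---|---|
| (a) GCBT gain fades | 0, -.25, -.5, -.5, -.5 | 0, -.6, -1, -.75, -.5 | .5/.5 = 1 | 1/.5 = 2 |
| (b) SGP catches up gradually | 0, -.25, -.5, -.75, -1 | 0, -.5, -1, -1, -1 | .5/1 = .5 | 1/1 = 1 |
| (c) SGP catches up by 3 months | 0, -.25, -.5, -1, -1 | as (b) | .5 | 1 |
| Persisting | as SGP in (a) | as GCBT in (b) | 1 | 1 |

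Only the persisting case has one ratio, so only there can the model fit both arms.

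**Fitted 6-month slope effect and rejection rate.** Two-level maximum likelihood fit, likelihood-ratio test, 600 trials per cell, Monte Carlo SE up to 2.0 points. Values are in the order of the three correlation structures; positive favours GCBT.

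| Case | True 6-month difference | Fitted slope effect | Significant |
|---|---|---|---|
| (a) | 0 | .272 / .294 / .281 | 58.7 / 36.0 / 54.3% |
| (b) | 0 | .138 / .210 / .152 | 11.2 / 18.0 / 13.0% |
| (c) | 0 | -.013 / -.034 / -.012 | 6.5 / 9.8 / 8.3% |
| Persisting | .5 | .500 / .514 / .517 | 85.5 / 69.3 / 80.0% |
| Null (both arms as SGP in (a)) | 0 | – | 4.7 / 5.7 / 5.3% |

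A repeat fit at population level returned the same slope effects in (a) to (c) and in the persisting case.

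**Change versus level in (c).** The fitted post-treatment difference in change is b·λ_post: -.013 × .77 = -.010, -.034 × .72 = -.024 and -.012 × .73 = -.009. That is about 0, against a true .5. The fitted difference in level at post-treatment is .12-.14, but this is almost entirely a fitted baseline gap of .138-.152 that does not exist in the assumed data.

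**Visit-specific alternative.** The baseline-adjusted 6-month contrast (4,000 trials) is significant in about 5% of trials in (a) to (c). If .5 persists, its power on the same 600 trials as the slope test is 82.0 / 73.8 / 77.2%.

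**The case against.** The plan is less silent than it may seem. Treatment is said to predict change over active treatment and follow-up, and the slope carries change for whatever interval is of interest. Slope-on-treatment is therefore the evident coefficient, and one model per interval is permitted. The worked example ends at post-treatment and is sound there. The constraint bites only with one model through 6 months, intermediate visits kept, common loadings and no arm difference in the intercept.

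The trajectories are invented, and material false persistence appears mainly in (a). The one durability result in the documents, the motor vehicle accident pilot, reports gains maintained at 3 months, though in another population and without a follow-up comparison. In (a) the fitted post-treatment loading is about 1.5 under two of the three correlation structures, which would alert a careful analyst; under the autoregressive structure it is 1.04 and would not.

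Most of this stands, and it limits the point to the follow-up part of Hypothesis 1. It does not supply the missing model or rule. A separate 6-month model that keeps the intermediate visits still carries the constraint.

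A reader might infer that Hypothesis 1 has no valid test at all, or that the planned test is generally anti-conservative. The documents do not support the first, since the post-treatment model is usable. The second is contradicted by the 5-6% rejection under the null. Nor does the plan ignore clustering of change, since it nests the slope as well as the intercept under treatment groups.

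**Conclusion.** The concern holds for the follow-up part of Hypothesis 1 and should be fixed. The absence of a persistence rule follows from the text alone. The proportionality constraint is exact under the conditions given, of which common loadings are implied and not stated.

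Its size depends on assumed trajectories and complete data, although section D expects missing data. With a true 6-month difference of 0, the false carry-forward is substantial if the GCBT gain fades (0.27-0.29 SD, significant in 36-59% of trials), modest if SGP catches up gradually (0.14-0.21, 11-18%), and close to nominal if SGP catches up by 3 months (about 0, 7-10%).

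In the last case a reader might take the 0.12-0.14 level difference as a shrunken treatment effect. It reflects the spurious baseline gap; the fitted difference in change is about 0. Loss of the post-treatment effect matters only if one model serves both claims, which the plan's example does not suggest. When the effect persists, the model recovers 0.50-0.52.

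Hypothesis 4 inherits the gap because it reuses the same approach. Hypothesis 3 does so only where it claims a 6-month arm difference.

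**What to change.** For the follow-up part of Hypothesis 1:

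- Let the arm difference vary freely by visit, either with treatment-by-visit means or, in Mplus, with direct treatment paths to the visits in place of the slope path.
- Keep treatment-group clustering on both baseline level and change, as the plan already intends.
- Name the baseline-adjusted GCBT-SGP contrasts at post-treatment, 3 and 6 months.
- State in advance which contrast or contrasts decide persistence. Requiring all three at p < .05 is one option; it declares persistence in 1-3% of trials in (a) to (c), but lowers power to 65-71% when 0.5 SD persists.

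Apply the same to Hypothesis 4 and, where it claims a 6-month arm difference, to Hypothesis 3, after reconciling their windows. For Hypothesis 4, section A has "a between-group difference that will persist through *3 month* follow-up", while D.4 and D.7.a run to 6 months. For Hypothesis 3, D.4 claims larger reductions "at post-treatment assessment and 3- and 6- month follow up", while A and D.7.a speak only of stability at 6 months.

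The cost is SAP wording and a different model statement, with the same data and software. If 0.5 SD persists, power of the single 6-month contrast is 74-82%, against 69-86% for the slope test. By correlation structure the change is 82.0 - 85.5 = -3.5, 73.8 - 69.3 = +4.5 and 77.2 - 80.0 = -2.8 points.

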### **Outcome variables:**

**Measures of PTSD symptoms** will include the Clinician Administered PTSD Scale - 5 (CAPS -5) and the Posttraumatic Check List - 5 (PCL-S-5). The CAPS-5 has been discussed in Section D1 (Study Participants). The CAPS-5 will serve as the primary outcome measure for PTSD. Both measures derived from the CAPS-5 will be used (presence/absence of PTSD diagnosis and overall PTSD severity score

Other measures include:

- The PTSD Checklist-5 (PCL-5; Weathers, Litz, Huska, & Keane, 1994) is self-report measure of PTSD, that corresponds to the DSM-5 symptoms of PTSD. Like the CAPS, the PCL can be scored to yield an overall severity score (total score). Psychometric properties of the prior PCL are sound (Weathers et al., 1994). The proposed project will use the PCL-S-5, a version that requests individuals to state the index event for which they are rating symptoms. In addition to the assessment map provided in Table 4, the PCL5 will be administered weekly during treatment, in order to track participant risk. Greater details about how the PCL data will be used to assure participant safety can be found in Section E.2.

**Measures of distress and impairment** Three subscales of the Medical Outcomes Study Short-Form Health Survey (SF-36; Ware & Sherbourne, 1992) will be used to index objective role functioning/impairment. These scales are the Role Limitations due to Physical Problems (role-physical), Role Limitations due to Emotional Problems (role-emotional), and Social Functioning subscales which appear to be minimally confounded with psychopathology. All three of these subscales have shown factorial validity and discriminative validity (Ware & Sherbourne, 1992).

- **Health care utilization** will be examined as an exploratory aim to investigate the effect of PTSD group treatment on health care utilization. This measure will be evaluated via record tracking. Veterans may obtain medical care within or outside of the VA system. When men initially enroll in the project, we will ask the names of their medical providers. Physician records in the VA system can be electronically accessed using the CPRS system. For physicians outside of the VA system, we will seek a signed release of information, which will permit contact to track the number of visits. The Project Coordinator will keep monthly records of the number of medical visits (excluding wellness visits) for each participant.

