**Is this RCT adequately statistically powered?** In the study design, several factors were involved in determination of sample size. **First**, we drew estimated effect sizes from the **two** pilot studies on GCBT and from a recent meta-analysis (Bradley et al., 2005). Within the MVA pilot study, which contrasted GCBT with a minimal contact comparison condition, effect sizes for PTSD measures ranged from .83 to 1.04 (Hedges's unbiased  $g$ , Hedges, 1981). Within our Vietnam veteran pilot data, the pre-post treatment effect size for the PCL-M was  $d = 1.43$ . Consulting the larger literature, Bradley et al. (2005) computed average effect sizes (Cohen's  $d$ ) of .84 for contrasts between CBT versus supportive therapy conditions and 1.01 for contrasts between ET + cognitive therapy versus supportive therapy conditions. However, in RCTs involving veterans, effect sizes tend to be smaller, owing to the chronicity and severity of combat-related PTSD in this population. In computation of sample size for this trial, we have selected a relatively low value of  $d$  (.50); review of available studies (including our own pilot data) suggests effect sizes ranging from 0.84 to 1.43. Recognizing that effect sizes for contrasts between CBT and supportive psychotherapy tend to average  $d = .84$  (Bradley et al., 2005), that data from samples with chronic PTSD tend to have smaller effects, relative to less severe samples, and that effect sizes drawn from relatively small samples can be unstable, we took a conservative stance in estimating the effect size for the GCBT versus SGP contrast to arrive at  $d = .50$ . **Second**, because treatment within both conditions of this RCT will occur in groups, the analytic plan must account for the cluster effect owing to the correlation of outcomes within groups (expressed as  $\rho$ , the intraclass correlation coefficient). There is one clustered variable in this design (individuals within groups) which will be adjusted for in determining sample size. Following guidelines provided by Hsieh (1988) and Diggle et al. (2002), we used an inflation factor that was driven by the  $\rho$  values from the MVA-related PTSD pilot data. In particular, the  $\rho$  estimate of 0.11 is a conservative assumption, based on the largest value obtained in the pilot MVA study. In the pilot MVA study ([name] et al., 2009), the  $\rho$  for the CAPS was 0.07, the  $\rho$  for the BDI-II was 0.03, and for the BAI, the  $\rho$  was 0.08. Within the Collaborative 420 study (Schnurr

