In addition to statistical significance, we were concerned about the potential clinical significance of these data. Presently, there is no agreed-upon effect size that is thought to be clinically significant. This is difficult to determine because effect sizes hinge on many variables (e.g., the size and nature of the sample, the amount of variance in the assessment strategy, the amount of variance in treatment administration). In our power calculations, we have relied on a .80 power level, to have a sufficient sample size for this RCT for statistical significance. Unfortunately, there is no consensus in the treatment literature regarding what constitutes a clinically significant effect size; Friedman and colleagues (2006) suggest that clinically meaningful differences between 2 active treatments would be illustrated by an effect equal to or greater than .30 (Cohen's  $d$ ). Consultation with [name] (Project Statistician) thus indicates that the proposed  $n$  will be sufficient to determine whether GCBT produces clinically meaningful outcomes.

**Analytic approach:** Data from both sites will be combined prior to analyses. [name], the Project Statistician, will work in close collaboration with [name] to perform the analyses. Prior to testing hypotheses, the outcome data will be examined to assess if they meet the assumptions for the proposed statistics (Tabachnick & Fidell, 2001). If the assumptions are not met (e.g., the data depart from normality, multivariate outliers are present), appropriate data transformations will be used. Additionally, the GCBT and SGP groups will be examined for pre-treatment differences, to test for group equivalency. These analyses will involve a series of independent  $t$ -tests on each of the outcome measures as well as demographic variables. Pre-treatment differences between conditions will be incorporated into the models used to examine the primary hypotheses, as described below.

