subscales of the CALPAS), (3) treatment credibility, and (4) homework compliance, defined as the percentage of homework that the veteran completes, as well as the quality of that homework as rated by the therapists. For analyses involving the number of sessions attended, group alliance, and treatment credibility, we will use data from both the GCBT and *SGP* conditions.

Number of sessions attended will range from 1-14 for patients in both conditions. For group psychotherapy alliance, the CALPAS will be used. For treatment credibility, the four items from the treatment credibility measure (administered following session 1) will be summed to form a composite score. These analyses will examine the direct and moderating effects of each of these variables on variation in treatment response using the CAPS Total score as the outcome. The same multilevel latent growth modeling approach described earlier will be used, bringing these variables into the analysis as additional predictors of within (individual) and between group (treatment groups) variability in symptom change. Of particular interest will be the possibility of significant interactions between each variable and treatment condition (e.g., a significant Treatment Condition x Alliance product term), which would indicate that the strength of effect of these variables on treatment outcome differs between the GCBT and *SGP* conditions (e.g., group alliance is more strongly related to treatment response in the *SGP* condition than the GCBT condition).

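### Fitting the CAPS and PCL models separately does not estimate or test the respondent effect the plan says it will examine

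*Combined protocol and SAP*

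**What the plan says.** Section D.4 sets the hierarchy: "The CAPS-5 will serve as the primary outcome measure for PTSD". In D.7.a, Hypothesis 1 is tested with a multilevel latent growth model for a single outcome: "The dependent variable for this analysis is the CAPS total score". The next sentence adds the self-report measure and gives the reason: "PCL will be examined, using the same analytic approach, in order to examine respondent effects (interviewer-rated versus self-report".

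No section describes a joint model of the two measures, a measure-by-condition term, an equality constraint across the two treatment effects, a common scale for CAPS and PCL, or a rule for deciding that a respondent effect is present.

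Elsewhere the plan does specify direct tests of contrasts. Under Hypothesis 2 it constrains the 6- and 12-month loadings to be equal and compares model fit. In D.7.d, for the process variables and homework compliance, it plans product terms with condition: "Of particular interest will be the possibility of significant interactions between each variable and treatment condition".

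**The concern.** The stated purpose is a comparison between two measures, but the stated method is two comparisons between arms. One significant and one non-significant result does not show that the effects differ. Two significant results do not show that they agree. Both scores come from the same men, so the difference between the two effects can be estimated directly, using the correlation between them.

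The comparison is worth making properly. Assessors are blinded to condition (D.1), whereas the PCL is completed by men who have sat in the treatment group. A gap between the two measures would bear on reporting or expectation bias and would probably be discussed in the trial report. As written, the analysis could suggest a gap that is not there or miss one that is.

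**Working it through.** **Inputs from the documents**
- 98 men per arm, in 14 groups of 7 per condition.
- Planning effect d = 0.50. The power section also cites, as clinically meaningful between two active treatments, an "effect equal to or greater than .30", so d = 0.30 is used too. The meta-analytic average for CBT against supportive therapy is 0.84.
- ICC: "estimate of 0.11 is a conservative assumption, based on the largest value obtained in the pilot MVA study". In that pilot the value "for the CAPS was 0.07", and in the earlier VA cooperative group-therapy trial it was 0.05.
- p < .05. Sidedness is not stated, so two-sided is assumed.

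**Input not in the documents**
- r, the correlation between the CAPS and PCL treatment-effect estimates. Assumed 0.5 to 0.8, with 0.9 and 0 as extremes.

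**The plan's own figure.** The respondent-effects sentence has no figure of its own; the only related one is N = 196. Without clustering, n per arm = 2 × (1.960 + 0.842)² / 0.50² = 63. The design effect is 1 + 6 × 0.11 = 1.66. Then 63 × 1.66 = 105 per arm, or 210 in total, so 196 is not reproduced. That is a separate matter and does not affect this point. At 98 per arm the power is 77.5%.

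**Standard error of one standardised effect.** SE = √(2 × design effect / 98):
- ICC 0.11: √(2 × 1.66 / 98) = 0.184
- ICC 0.07: √(2 × 1.42 / 98) = 0.170
- ICC 0.05: √(2 × 1.30 / 98) = 0.163

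**Chance that exactly one model is significant when the true effects are identical.** This is 2 × (P1 − P12). P1 is the power of one test. P12 is the probability that both are significant, from a bivariate normal with means d/SE and correlation r. For d = 0.50 and ICC 0.11, d/SE = 2.717 and P1 = 0.775.
- r = 0.5: P12 = 0.654, giving 2 × (0.7753 − 0.6537) = 0.243
- r = 0.8: P12 = 0.699, giving 2 × (0.7753 − 0.6992) = 0.152

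| ICC | d = 0.50; r = 0.5 / 0.7 / 0.8 | d = 0.30; r = 0.5 / 0.7 / 0.8 |
|---|---|---|
| 0.11 | 24% / 19% / 15% | 31% / 24% / 19% |
| 0.07 | 20% / 15% / 12% | 33% / 25% / 20% |
| 0.05 | 17% / 13% / 11% | 33% / 25% / 20% |

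At ICC 0.11 and d = 0.50 the extremes are 11% (r = 0.9) and 35% (r = 0). At d = 0.84 the rate is under 1% for every ICC and r used. With no effect on either measure it is 4-10%.

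**Simulation check.** With 14 groups of 7 per arm, ICC 0.11 and a cluster-mean t-test on 26 df, the rates are 27%, 21% and 17% at d = 0.50 (r = 0.5, 0.7, 0.8) and 32%, 24% and 20% at d = 0.30. A direct test of the difference was falsely significant in 4.9-5.2%.

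**The opposite error.** If the true effects were 0.50 on CAPS and 0.80 on PCL, both tests would be significant in about 77% of trials at ICC 0.11. A reader comparing significance would see agreement.

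**Precision of a direct contrast at ICC 0.11.** SE of the difference = 0.184 × √(2(1 − r)):

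| r | SE | 95% CI half-width | Power for a 0.30 SD gap |
|---|---|---|---|
| 0.5 | 0.184 | 0.36 | 37% |
| 0.7 | 0.143 | 0.28 | 56% |
| 0.8 | 0.116 | 0.23 | 73% |

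Comparing the two estimates as if independent would give an SE of 0.184 × √2 = 0.260.

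**The case against.** The plan only says the PCL will be examined. It does not say that a respondent effect will be declared when one p-value falls below .05 and the other does not, and its models will supply estimates and confidence intervals for both measures. A reader might infer that 11-24% is an error rate of the plan. The documents do not support that: it is the rate at which someone comparing significance would be misled. The rate also depends on an assumed r, is lower at the CAPS ICCs the plan reports than at 0.11, and is only 4-6% at ICC 0.11 if the effect equals the 0.68 average for group CBT quoted in B.2. All of this stands. Even so, two intervals placed side by side do not give the interval for their difference.

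A reader might also infer that this is the plan's only check on expectation effects. It is not. D.4 collects a credibility measure after Session 1 that covers expectations of success, and D.7.d examines it as a predictor and moderator of CAPS outcome, with a condition product term.

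A direct contrast has limits too. With 37-73% power for a 0.30 SD gap, a non-significant result would still often reassure wrongly unless the interval is read. Scaling matters as well: CAPS-5 is the entry instrument and the Randomization section expects little spread in baseline CAPS. If selection cut the CAPS baseline SD to 80% of its unrestricted value, equal effects of 0.50 would appear as 0.50 / 0.80 = 0.63 against 0.50. The contrast also mixes who reports with which instrument is used. These points shape the fix but do not remove the need for one.

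**Conclusion.** The concern holds in a limited form. The plan sets a comparative aim and supplies no estimate or test for it, although it plans direct tests for other contrasts and its modelling framework could accommodate this one. For a reader who compares significance, identical true effects would look different in about 11-24% of trials at d = 0.50 and about 19-33% at d = 0.30, against 5% for a direct test. This rests on ICCs of 0.05-0.11, r of 0.5-0.8 and two-sided testing. The problem all but vanishes at d = 0.84.

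It would be wrong to read this as a threat to the primary result. No hypothesis concerns respondent effects, CAPS-5 remains primary, and its test and sample size are untouched. The PCL is a legitimate supportive outcome. This is a secondary-analysis gap that should be closed.

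**What to change.** Add one pre-specified secondary contrast to D.7.a. Either fit CAPS-5 and PCL-5 together in a bivariate (parallel-process) multilevel growth model and estimate the difference between the two condition-to-slope paths on a common scale, or use the standardised CAPS-minus-PCL score as the outcome in the Hypothesis 1 model. Report the arm-by-measure difference mainly as an estimate with a 95% CI.

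Name the scaling in advance and do not rely on baseline SDs alone. Repeat the contrast under a second scaling, for example pooled post-treatment SDs, as a sensitivity check. State that the contrast combines respondent and instrument differences.

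If the investigators do not want this analysis, they should call the PCL a supportive outcome and delete the respondent-effects claim.

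The cost is a few lines of analysis-plan text and one extra model (plus its repeat under the second scaling) on data already scheduled for collection. The downside is a contrast of only moderate precision.
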